The trial is conducted in accordance with International Conference on Harmonisation Good Clinical Practice (ICH GCP) and applicable United States (US) Code of Federal Regulations (CFR). The Principal Investigator assures that no deviation from, or changes to, the protocol will take place without prior documented approval from the Institutional Review Board (IRB), except where necessary to eliminate an immediate hazard(s) to the trial subjects. All personnel involved in the conduct of this study have completed Human Subjects Protection and ICH GCP Training.

The protocol, informed consent form(s), recruitment materials, and all subject materials are submitted to the local Institutional Review Board (IRB) for review and approval. Approval of both the protocol was obtained before any subject was enrolled. Any amendment to the protocol required review and approval by the IRB before the changes were implemented to the study.

1 PROTOCOL SUMMARY

1.1 SYNOPSIS

Title:	Increasing recruitment of underrepresented cancer survivors with awareness enhancing interventions (AWEI)
Study Description:	
This study aims to investigate whether increasing awareness and, thus, enhancing positive attitudes about research, prior to recruitment attempts, will increase participation in cancer clinical research among African American (AA) cancer survivors
 
Specifically, we investigate if interventions to raise awareness about research can increase the recruitment of African American cancer survivors to a web-based diet and physical activity interventions trial, known as the Adapting MultiPLe behavior Interventions that eEffectively Improve (AMPLIFI) Cancer Survivor Health trial (NCT04000880). The study will use a factorial trial design to test the effectiveness of the Awareness and Willingness to Engage in Research Intervention (AWEI) versus the original AMPLIFI recruitment strategy.

Objectives:	To determine if interventions to raise awareness about research can increase the recruitment of African American cancer survivors to the AMPLIFY web-based diet and physical activity trial
Endpoints:	
– Reached = whether the AMPLIFI recruiter was able to reach the potential participant over the phone– Screened if reached = whether the survivor who was reached by the recruiter was willing to consider the study and to be screened to ascertain eligibility for the AMPLIFI trial

	
 – Consented if eligible = whether the survivor who was screened and found eligible to participate in the AMPLIFI trial agreed and consented to participate in the AMPLIFI trial
Study Population:	
Adult (age ≥ 50 years old) African American cancer survivors who were eligible for enrollment into the AMPLIFI trial
 
 - Within 1-5 years from a diagnosis of loco-regional cancers of the colorectum, female breast, prostate, endometrium, localized kidney or ovarian cancer, thyroid cancer, multiple myeloma and non-Hodgkin's lymphoma
Phase:	2
Description of Study Intervention:	
The AWEI interventions were educational interventions that varied by:
 
 - delivery channel, i.e., education through a brochure vs. a research educator 'navigator' - research emphasis, i.e., highlighting the importance of participating in AMPLIFI vs. in research in general - perspective, i.e., the information reflected the voice of a cancer survivor vs. that of an expert researcher
Study Duration:	3 years
Subject Duration:	15 days

2 INTRODUCTION

2.1 STUDY RATIONALE

African American cancer survivors are often underrepresented in clinical trials, which can limit the generalizability of research findings. This study seeks to address this gap by testing an intervention designed to increase awareness and willingness to participate in a web-based diet and physical activity trial.

2.2 BACKGROUND

As highlighted in the 2022 National Academies of Medicine report on improving representation in clinical trials and research, the lack of representation of diverse groups has many consequences including hindering innovation and new discoveries, generalizability of research findings, access to effective medical interventions, and trust in research and medicine. Inadequate representation in research means we have limited information and opportunity to advance knowledge to reduce the cancer burden

and to understand underlying causes of disparate outcomes across different groups. This is highly significant for African Americans who have the highest death rates of all racial and ethnic groups for about half of the most common cancers.

Increasing awareness among cancer survivors about the importance of research and study participation may be a key, yet often overlooked approach to achieving more racially/ethnically diverse trials. Many questions exist about the best ways to convey the relevant information to potential participants. For example, while lay navigator interventions are promising, they are also costly: whether more economical interventions, e.g., using brochures conveying the same information, are effective is unknown. Other questions are related to whether it would be more effective to raise awareness about the specific study recruiting participants or about the importance of research in general, and whether this should be done conveying the information from the perspective of the survivor or the researchers.

2.3 RISK/BENEFIT ASSESSMENT

2.3.1 KNOWN POTENTIAL RISKS

Risks and discomforts from participation in project activities for the AWEI trial are no greater than those associated with day-to-day living. No medical tests or procedures will be conducted, and no social, legal or other risks are anticipated.

2.3.2 KNOWN POTENTIAL BENEFITS

Survivors participating in this project may benefit from increasing their awareness about research, and better understanding the importance of participating. They will be better able to make an informed decision about the opportunity to participate in the AMPLIFI trial. The findings will benefit the research community as evidence for recruitment methods are scarce especially for increasing the recruitment of minorities.

3 STUDY DESIGN

3.1 OVERALL DESIGN

This is a prospective interventional study using a randomized factorial trial design. Participants will be randomized to one of 8 combinations of the AWEI intervention or to the control group (no AWEI) (Table 1). The AWEI intervention varies by type of delivery channel (Research Educator [RE] and Brochure), information emphasis (research general information vs. AMPLIFI study specific information), and type of perspective (information presented from a researcher or a survivor perspective).

Table 1: AWEI study design and randomized control trial (RCT) arms

	Features			AWEI combination
	Delivery channel	Information emphasis	Perspective	
Awareness Enhancing Interventions (AWEI)	Research Educator	Research general	Researcher	1
			Survivor	2
		Study specific	Researcher	3
			Survivor	4
	Brochure	Research general	Researcher	5
			Survivor	6
		Study specific	Researcher	7
			Survivor	8
No AWEI	--	--	--	

4 STUDY POPULATION

4.1 INCLUSION CRITERIA

[figure not shown]
African American cancer survivors who were eligible for enrollment into the AMPLIFI trial

- adults (age ≥ 50 years old)
- within 1-5 years from a diagnosis of loco-regional cancers of the colorectum, female breast, prostate, endometrium, localized kidney or ovarian cancer, thyroid cancer, multiple myeloma and non-Hodgkin's lymphoma

4.2 EXCLUSION CRITERIA

- Not identified for recruitment to AMPLIFI trial

4.3 STRATEGIES FOR RECRUITMENT AND RETENTION

The AWEI trial was embedded into the AMPLIFI trial's recruitment process.² To identify the list of eligible survivors, AMPLIFI collaborated with the Alabama Statewide Cancer Registry (ASCR) and the North Carolina Registry (NCR), and followed their protocols for the release of contact information to the AMPLIFI research team. The AMPLIFI process started with survivors receiving a recruitment letter informing them about the study and of the possibility of receiving a call from an AMPLIFI recruiter. Survivors were also given the team's contact information to opt-out from the study if they so wished.

The AWEI trial randomization occurred once the recruitment letter was sent. No retention strategies were necessary since participation in the AWEI trial lasted 15 days. Outcomes were assessed as part of the AMPLIFY trial.

5 STUDY INTERVENTION

5.1 STUDY INTERVENTION(S) ADMINISTRATION

5.1.1 STUDY INTERVENTION DESCRIPTION

AWEI interventions were educational interventions delivered through a research educator or a brochure.

5.1.2 DOSING AND ADMINISTRATION

In the AWEI-Research Educator (RE) arm, one of four REs attempted to contact survivors by phone starting 5 days after the letter was sent (7 attempts over 10 days) and deliver the content of the intervention following a script. Each RE was trained on the

script of one of the AWEI-RE combinations differing by Information Emphasis and Perspective to avoid contamination across AWEI groups. If the survivor did not receive the recruitment letter, the RE would give more information about the purpose of the call and offer to resend the letter.

In the AWEI-Brochure arm, one of 4 brochures according to AWEI combination was sent 4 days after the recruitment letter was sent. The same content was delivered in the AWEI-RE and AWEI-Brochure arms.

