7 STUDY ASSESSMENTS AND PROCEDURES

7.1 STUDY ASSESSMENTS

AWEI study outcomes are tracked and recorded by AMPLIFI recruiters who are blind to the AWEI random assignment. No other assessments are conducted.

To allow for the AWEI interventions to be delivered, we allow 15 days from the time from when the recruitment letter was sent to when the AMPLIFY recruitment call occurred.

To further ensure that AMPLIFY recruiters remain blind to study assessment, AWEI participants, including those in the no AWEI control arm, are “released” to the recruiters in a random fashion over the 15 days AWEI period starting at day 8. For the AWEI RE arm, survivors are released after the RE call is completed or the RE completed all 7 attempts to deliver the intervention.

Survivors reached by AMPLIFY recruiters are given more information about the study and given the option to be screened for participation to verify additional inclusion (e.g., completed primary treatment) and exclusion criteria (e.g., conditions that would make unsupervised exercise unsafe). If they screen eligible and are interested in joining AMPLIFY, they would undergo the informed consent process and enroll in AMPLIFY.

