8 STATISTICAL CONSIDERATIONS

8.1 STATISTICAL HYPOTHESES

- Primary Efficacy Endpoint(s):

Recruitment yield assessed by:

1) Consented if eligible: Binary indicator of whether the survivor who is screened and found eligible to participate in the AMPLIFY trial agrees and consents to participate in the AMPLIFY trial.

- Secondary Efficacy Endpoint(s):

Interest in participating in the AMPLIFY study and returned their consent assessed by:

Same as recruitment yield.

Post Hoc Outcomes:

- 1) Reached: Binary indicator of whether the AMPLIFY recruiter is able to reach the potential participant over the phone, regardless of whether the survivor is willing to receive information about AMPLIFY
- 2) Screened if reached: Binary indicator of whether the survivor who is reached by the recruiter is willing to consider the study and to be screened to ascertain eligibility for the AMPLIFY trial

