8.2 SAMPLE SIZE DETERMINATION

Hypothesis 1: AWEI (any combination) will have a significantly higher recruitment yield than the basic AMPLIFY recruitment strategy (no AWEI control group).

With a minimum of 1,600 in the AWEI intervention group, and 400 in the no AWEI control group, a two-sided chi-square test (for unequal sample sizes), and a 5% significance level, we will have > 95% power to detect a statistically significant difference in recruitment yield of 10% vs. 20%.

Hypothesis 2 - Delivery channel: AWEI-Research Educator will have a significantly higher recruitment yield than AWEI-brochure

Hypothesis 3 - Information emphasis: Education content with study-specific emphasis will have a significantly higher recruitment yield than with research general emphasis

Hypothesis 4 - Perspective: Education content delivered from the survivor perspective will have a significantly higher recruitment yield than education content delivered from the researcher perspective.

For these hypotheses, with a minimum of 800 per group, a two-sided chi-square test, and a 5% significance level, we will have > 95% power to detect a statistically significant difference in recruitment yield of 10% vs. 20%.

Hypothesis 5: AWEI-Research Educator with study-specific emphasis and cancer survivor perspective (combination #3, Table 1) will be the most efficacious.

The same sample size calculation applies to the comparison of any two combinations. With a minimum of 200 per group, a two-sided chi-square test, and a 5% significance level, we will have 80% power to detect a statistically significant difference in recruitment yield of 10% vs. 20%.

Calculations were performed using nQuery Advisor + nTerim, version 3.0.

Thus, the trial is fully powered with a sample of 2,000 survivors, 200 in each AWEI combination, and 400 in the no AWEI arm. However, we will randomize all survivors identified from the cancer registries. If these are less than 2000, we will expand to other

cancer registries (estimated numbers from these registries exceed 2000 survivors). If these are more than 2000, we will randomize all.

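### Each research educator delivers only one of the four telephone scripts, so within that arm the results for Hypotheses 3 to 5 mix caller and content, and the plan neither reports the educator-free brochure contrast nor limits the content claim.

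*Combined protocol and SAP*

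**What the plan says.** **Delivery.** Section 5.1.2 states that "one of four REs attempted to contact survivors by phone starting 5 days after the letter was sent", and that each was trained on the "script of one of the AWEI-RE combinations differing by Information Emphasis and Perspective to avoid contamination across AWEI groups". Table 1 (Section 3.1) lists four RE combinations, numbered 1 to 4, and four brochure combinations, numbered 5 to 8. On the brochures, Section 5.1.2 adds: "The same content was delivered in the AWEI-RE and AWEI-Brochure arms".

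**Hypotheses.** Section 8.2 frames Hypothesis 3 as "Education content with study-specific emphasis will have a significantly higher recruitment yield than with research general emphasis" and Hypothesis 4 as "Education content delivered from the survivor perspective will have a significantly higher recruitment yield than education content delivered from the researcher perspective". Neither is restricted to a channel or an educator. The sample size reads "For these hypotheses, with a minimum of 800 per group, a two-sided chi-square test, and a 5% significance level", which for Hypotheses 3 and 4 means pooling 400 RE and 400 brochure survivors at each level. Hypothesis 5 names one RE combination as the best of all.

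**Analysis.** Section 8.3.1 leaves Hypotheses 3, 4 and 5 to later logistic regression without naming model terms. Section 8.3.2 sets out comparison groups only for Hypotheses 1 and 2. Neither section mentions an educator effect, a channel-by-content term, a brochure-only contrast or a limit on interpretation.

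**Endpoint.** The primary endpoint in Section 8.1 is a "Binary indicator of whether the survivor who is screened and found eligible to participate in the AMPLIFY trial agrees and consents", so the analysed denominator is smaller than the number randomised.

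**The concern.** If one educator reads one script, a difference between two scripts in the RE arm is also a difference between two people. Randomising survivors does not help, because the educator comes with the assigned cell. In the RE arm, the emphasis contrast (3+4 vs 1+2), the perspective contrast (2+4 vs 1+3) and every comparison between two of these cells therefore estimate an educator-plus-script effect.

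Hypotheses 3 and 4 are meant to tell recruiters which message to use. If educators differ in how they influence later consent, part of that difference will be reported as the merit of study-specific content or of the survivor voice. A reader could not tell a better script from a more persuasive caller. The brochure cells carry the same content with no caller, so the design already holds an educator-free contrast, but the plan does not call for it.

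**Working it through.** **1. The plan's own figures.** For two groups of n, with p̄ the mean of the two rates:

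power = Φ{ [|p1 − p2| − 1.96 √(2p̄(1 − p̄)/n)] / √([p1(1 − p1) + p2(1 − p2)]/n) }

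For 10% vs 20% this gives 99.99% at 800 per group (plan: above 95%) and 80.2% at 200 per group (plan: 80%). The stated power is arithmetically right. The question is what the contrasts identify.

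**2. Identifiability.** In combinations 1 to 4, four script indicators plus four educator indicators form a design matrix of rank 4, not 7. The two sets of columns coincide, so no covariate, random effect or larger sample can separate them.

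**3. Size, by assumption.** The documents give no educator variance, yield, reach rate or analysed count per cell. Assumed here: no content effect, base yield 15%, and a normal educator effect on the log-odds with variance ICC/(1 − ICC) × π²/3, drawn once for each of combinations 1 to 4.

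- At ICC 0.01 the variance is 0.0101 × 3.29 = 0.0332, so SD = 0.182. Educators one SD either side of average have yields of 12.8% and 17.5%.
- On the probability scale the SD is about d = 0.15 × 0.85 × 0.182 = 0.0232, so d² = 0.00054.
- Pooled contrast, 200 per cell: sampling variance 2 × 0.1275/800 = 0.000319. Each level averages four cells, two of them RE, so the educator variance is 2 × 2d²/16 = d²/4 = 0.000135. Variance ratio 1.424; rejection rate 2Φ(−1.96/√1.424) = 10.0%.
- RE-only contrast, 200 per cell: sampling variance 2 × 0.1275/400 = 0.000638, educator variance d² = 0.00054. Ratio 1.847; rejection rate 14.9%.

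Simulation (400,000 trials per setting, uncorrected two-sided chi-square at 5%) agrees. Type I error at ICC 0.01:

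| Test | 200 per cell, all reached | 50 per cell, all reached | 50 per cell, half reached |
|---|---|---|---|
| Pooled H3 or H4 | 10.1% | 6.3% | 5.4% |
| RE-only H3 or H4 | 14.9% | 7.6% | 5.7% |
| One RE cell vs another | 15.0% | 8.0% | 6.1% |
| Brochure-only H3 or H4 | 5.0% | 5.1% | 5.0% |
| H2 (RE vs brochure) | 10.2% | 6.3% | 5.4% |
| H1 (any AWEI vs control) | 6.0% | 5.2% | 5.0% |

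At ICC 0 the cell-vs-cell test itself gives 5.0 / 5.6 / 5.4%, so part of its last two entries is small-sample behaviour of the chi-square test.

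Pooled H3 or H4 over ICC 0.001 / 0.005 / 0.02 / 0.05:

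- 200 per cell, all reached: 5.6 / 7.5 / 15.2 / 27.7%
- 50 per cell, all reached: 5.2 / 5.7 / 7.6 / 11.8%
- 50 per cell, half reached: 5.1 / 5.2 / 5.7 / 6.8%

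Under the 2,000-survivor plan, 200 per cell is an upper bound, because the endpoint counts only screened and eligible survivors.

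**4. What the brochure contrast offers.** Approximate 95% half-width = 1.96 √(2 × 0.15 × 0.85/n per group). Pooled vs brochure-only, this is 3.5 vs 4.9 percentage points at 200 per cell (n = 800 vs 400) and 7.0 vs 9.9 at 50 per cell (n = 200 vs 100). The ratio is √2 = 1.41. Power of the brochure contrast:

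| Analysed per group | 10% vs 20% | 10% vs 15% |
|---|---|---|
| 400 | 97.8% | 57.1% |
| 100 | 50.8% | 18.6% |
| 60 | 33.3% | 12.8% |

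**The case against.** **The arrangement is deliberate.** One script per educator prevents contamination between messages, and crossing educators with scripts would bring that risk back. This stands, and it is why the remedy lies in the reporting and not in the delivery.

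**The size may be negligible.** With 50 per cell and half reached, pooled error is 5.4% at ICC 0.01 and only 6.8% at ICC 0.05. Calls were scripted and Section 9.1.4 describes ongoing training. Section 7.1 also says "AWEI study outcomes are tracked and recorded by AMPLIFI recruiters who are blind to the AWEI random assignment". All of this may keep the effect small. Blinding, however, protects the recording of outcomes. It does not stop one educator from being more persuasive than another.

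**Inflation depends on the reading.** If the four educators are fixed parts of the intervention as delivered, the 5% level holds for each educator-plus-script package. That is correct. What remains is that the hypotheses speak of content, which is a broader claim than a package supports.

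**The brochure contrast is not a full answer.** It estimates the effect of printed content. If it differs from the RE contrast, the cause could be the educators or a true channel-by-content interaction, and if it agrees, low power makes the agreement weak evidence. It cannot settle Hypothesis 5, which concerns an RE cell. These limits stand, but it is still the only randomised content contrast free of educators.

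**Silence is not a contrary plan.** The analysis of Hypotheses 3 to 5 is deferred, so by-channel reporting is absent and not excluded. The manual of operations mentioned in Section 9.1.4 was not available and may say more about how educators were assigned.

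**Conclusion.** The concern holds and should be addressed. Within the RE arm, educator and script cannot be separated, and pooled estimates for Hypotheses 3 and 4 carry half of that confounding. As written, the plan would let educator-plus-script differences be reported as content effects.

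The structural point rests on one inference: four educators, four RE scripts and one script each imply a one-to-one match. The text does not rule out shared scripts or cover staff, but describes neither. The size rests wholly on assumptions. At ICC 0.01 the pooled error runs from 5.4% to 10.1% across the three settings, and the eligible-only denominator makes the upper figure a ceiling for that ICC under the 2,000-survivor plan. Hypothesis 2 is inflated much like the pooled tests, because its RE side rests on four people. Hypothesis 1 is little affected. Confidence is medium.

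**What to change.** Add to Section 8.3:

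> For Hypotheses 3 and 4 the pooled estimate is reported together with the brochure contrast (H3: 7+8 vs 5+6; H4: 6+8 vs 5+7) and the RE contrast (H3: 3+4 vs 1+2; H4: 2+4 vs 1+3), each with a 95% confidence interval. The RE contrast is described as an educator-plus-script effect and the brochure contrast as the estimate free of educator effects. A difference between the two may reflect educators or a channel-by-content interaction. For Hypothesis 5, differences among combinations 1 to 4 are not attributed to content alone.

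In addition:

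- Do not make brochure significance a condition for claiming a content effect.
- State as a limitation that the RE side of Hypothesis 2 rests on four educators.
- Reconcile Hypothesis 5 in Section 8.2, which labels the study-specific, survivor-perspective RE cell as combination 3, with Table 1, which lists it as combination 4. Until then the Hypothesis 5 cell is ambiguous.
- If power for the brochure contrast is quoted (97.8% for 10% vs 20%, 57% for 10% vs 15%), say that it assumes 400 analysed per group and is lower on the screened-and-eligible denominator (51% and 19% at 100 per group).

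The cost is text only: no extra staff, participants or data. The educator-free intervals are about 1.4 times wider than the pooled ones, and three estimates per hypothesis lengthen the report. Delivery and the three-group regression are described in the past tense, so the additions must be labelled post hoc if outcomes have already been seen.

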5.2 MEASURES TO MINIMIZE BIAS: RANDOMIZATION

All participants were randomized to the AWEI (the intervention group) and no AWEI (control group) using permuted block randomization. Those who were randomized to the AWEI arm were simultaneously randomized to one of 8 combinations using the same method (Table 1).

